AFRS

	1	
	BID	Twice a day
	CFR	Code of Federal Regulations
	CRSwNP	Chronic Rhinosinusitis with nasal polyps
	CT	Computed tomography
	EDC	Electronic Data Capture
	FU	Follow-up
	GCP	Good clinical practice
	ICF	Informed consent form
	IMP	Investigational medicinal product
	INCS	Intranasal corticosteroids
	IP	Investigational product
	IPD	IP discontinuation
	IRB	Institutional Review Board
	LMS	Lund-Mackay score
	mLK	Modified Lund Kennedy Endoscopic Score
	SNOT-22	SinoNasal Outcome Test, 22 item
	SoC	Standard of Care
	WOCBP	Women of childbearing potential
Funding	Sanofi	
Source		

Schema

2. Background

Allergic fungal rhinosinusitis (AFRS) is a severe form of eosinophilic nasal polyposis with critically inadequate treatment options for the 10% of chronic rhinosinusitis participants affected by the disease. Occlusive eosinophilic mucus and severe nasal polyposis presents in early adulthood, with an unrelenting course marked by sinus expansion and pressure-induced dehiscence of the surrounding orbit and skull base. Despite appropriate therapies with oral/topical corticosteroids, saline irrigations and comprehensive sinus surgery, nasal polyps aggressively recur, frequently within months of surgery. Medical options beyond topical and systemic steroids are limited. Neither antifungal nor allergen immunotherapy are beneficial. Due to persistent sinonasal inflammation, patients with AFRS receive an average of three corticosteroid bursts per year and revision sinus surgery every 42 months.

Rationale

In addition to the activation of type 2 inflammatory mediators found in other CRSwNP phenotypes, AFRS is uniquely characterized by an exaggerated activation of the adaptive immune response with serum IgE levels often above 1000 kU/L and defined by an upregulation of fungal specific IgE levels [1]. Marked eosinophilic inflammation is found throughout the upper airway, and the degree of mucosal eosinophil infiltration has been repeatedly reported as a potent predictor of poor surgical outcomes. We therefore hypothesize that dupilumab, a human monoclonal antibody that targets the type-2 inflammatory cascade, is a safe and effective treatment for nasal polyps as add-on therapy following endoscopic sinus surgery.

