3.2 Secondary Objectives

Secondary objectives	Endpoint/variable(s)	
	Change from baseline at 52 weeks both within	
	and between treatment and placebo arms	
To evaluate the effect of dupilumab on:		
Prevention of revision surgery for AFRS	Prevalence of revision sinus surgery for recurrent nasal polyps, and comparison of survival curves	
Secondary objective measures of sinonasal	• Endoscopic nasal polyp score (NPS)	
inflammation following sinus surgery	CT generated Lund-MacKay score	
• Lower airway dysfunction following sinus surgery in the subgroup of participants with asthma (~25%)	Spirometry	
• Upper and lower airway, disease-specific,	• 22-item sinonasal outcomes test (SNOT-22)	
health-related quality of life	Asthma Control Questionnaire (ACQ)	
Reducing utilization of rescue medications for acute exacerbations of CRS following sinus surgery	 Prevalence of oral / topical corticosteroid utilization per treatment cohort Incidence of oral / topical antibiotic utilization per subject Prevalence of oral / topical antibiotic utilization per treatment cohort 	

Other secondary objectives	Endpoint/variable(s)
	Change from end of treatment (EOT) to end of

	study (EOS)
To evaluate the effect of dupilumab on:	
Objective measures of sinonasal	Endoscopic modified Lund-Kennedy
inflammation following sinus	(mLK) score
surgery	• Endoscopic nasal polyp score (NPS)
• Upper and lower airway, disease-specific,	• 22-item sinonasal outcomes test (SNOT-22)
health-related quality of life	Asthma Control Questionnaire (ACQ)

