5.2.1 Objective measures of disease

Modified Lund-Kennedy Endoscopic Score:

Modified Lund-Kennedy score (mLK) is a validated measure of sinonasal inflammation, as evaluated by means of nasal endoscopy. The composite score ranges from 0 to 12, with increasing score representing worsening inflammation among three separate findings (Nasal polyps, Discharge, Edema). Each finding is rated from 0 (absent) to 2 (severe). $A \ge 2$ -point increase from baseline total postoperative score represents clinically significant worsening of sinonasal inflammation[5]. The treating physician will complete the nasal endoscopy per SoC,

with automated recording on local storage drives. Following completion of the patient encounter, study personnel will transfer this recording to the study database for central review and scoring. A blinded reader will review all nasal endoscopies to determine the mLK score.

Lund-MacKay Radiologic Score:

The change in radiographic opacification between baseline and EOT will be analyzed by the Lund- MacKay radiologic score (LM) [6]. The LM Radiologic scoring system assigns a value of 0, 1, or 2 to each of the following sinuses: maxillary, anterior ethmoid, posterior ethmoid, frontal, and sphenoid. Score assignments are 0 if the sinus is totally patent, 1 if the sinus is partially opacified, and 2 if the sinus is completely opacified. The osteomeatal complex is scored either 0 if not occluded or 2 if occluded. The maximum score for each side is thus 12, with a total score determined out of 24. Baseline LM scores will be assessed from baseline preoperative CT scan. Preoperative and EOT CT scans will be transferred to the study database by trained personnel, where the blinded reader may determine the associated LM score.

Endoscopic Nasal Polyp Score:

Endoscopic nasal polyp score is determined by the treating Investigator. Unlike prior study of dupilumab in nasal polyps, [7] we will separately record the Nasal Polyp Score for each side, with a maximum unilateral score of 4. This is appropriate for monitoring efficacy in AFRS, as a subgroup of participants may present with unilateral disease. This will be considered in statistical analysis and reporting of results (see Section 14.6- Primary Analysis).

Table 5: Endoscopic Nasal Polyp Score

Polyp Score	Polyp Size
0	No polyps
1	Small polyps in the middle meatus not reaching below the inferior border of
	the middle turbinate
2	Polyps reaching below the lower border of the middle turbinate

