- Discontinuing treatment: all data collected after discontinuation will be used in the analysis (treatment policy strategy)

We will examine the treatment effect in the subgroup of patients with unilateral disease by recording patients' time until next sinus surgery. We will investigate differences in this subgroup by examining the Kaplan-Meier curves and utilizing the log rank test of the difference between treated and non-treated. If there is a difference between survival times, we will use the Cox proportional hazard model to account for other relevant covariates such as disease severity.

The Bonferroni correction will be used to account for multiple testing and ensure Type-I error rate remains nominal.

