14.7 Secondary and Exploratory analyses

In a secondary analysis, a similar mixed model as described above will be fit that includes the subset of participants who are receiving treatment (dupilumab or placebo) for both nostrils. This model will incorporate nesting factors to identify repeated measures by subject and by nostril.

In an exploratory analysis, we will also compare the proportion of participants whose modified Lund- Kennedy score improved by greater than or equal to 2 units. For participants who undergo sinus surgery for AFRS prior to Week 52, non-responder imputation will be used. We will utilize a Chi-square or Fisher's exact test to examine if this proportion is significantly different by treatment group (dupilumab or placebo) at 52 weeks.

For the continuous secondary outcomes (e.g. SNOT-22 score, NPS, FEV1), a mixed effects longitudinal model will be fit that includes group (dupilumab, placebo), time (randomization through post-treatment period), and their interaction term in a similar fashioned as described for the primary outcome modified Lund-Kennedy score. For the secondary outcomes that compare the number of participants requiring rescue treatment and the number of adverse events (safety) over 52 weeks, similar mixed effects models will be fit but with consideration of a Poisson distribution (as opposed to normal distribution). The mixed effects models for both primary and secondary outcomes will permit the inclusion of any significant potential confounders.

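### Section 3.2 names a survival comparison for revision surgery without restriction, but the only survival method specified is confined to unilateral disease

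*Combined protocol and SAP*

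**What the plan says.** - **Objective and endpoint (Section 3.2; objective also in the Section 1 summary).** The first secondary objective is "Prevention of revision surgery for AFRS". Section 3.2 gives its endpoint as "Prevalence of revision sinus surgery for recurrent nasal polyps, and comparison of survival curves". Neither is limited by laterality.
- **Survival method (Section 14.6).** "We will examine the treatment effect in the subgroup of patients with unilateral disease by recording patients' time until next sinus surgery". The next sentence reads "We will investigate differences in this subgroup by examining the Kaplan-Meier curves and utilizing the log rank test". A Cox model with covariates follows only if survival times are found to differ.
- **Secondary methods (Section 14.7).** Continuous outcomes get a mixed model. A Poisson version is planned for the "number of participants requiring rescue treatment and the number of adverse events (safety) over 52 weeks". No time-to-event method appears.
- **Size of the subgroup (Section 5.2.1).** The plan says only that "a subgroup of participants may present with unilateral disease". It gives no proportion.
- **Background rate (Section 2).** AFRS patients are said to have "revision sinus surgery every 42 months" on average.

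**The concern.** The endpoint in Section 3.2 and the method in Section 14.6 apply to different populations. An analyst looking for the method behind the Section 3.2 comparison finds only one, and it applies to a subgroup of unstated size. Applied literally, it leaves participants with bilateral disease out of the log-rank test. Because the Cox model is fitted only when survival times differ, a null result would leave no hazard ratio or interval, even in the subgroup.

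Revision surgery is part of the trial's stated rationale. If the test, time origin, censoring rule and model for all randomised participants are chosen after unblinding, those choices can be challenged.

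**Working it through.** **1. The plan's own figure.** Section 14.1 gives 66 per group for 90% power (difference 2, SD 3.5, two-sided 0.05).

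n = 2 × (1.960 + 1.282)² × 3.5² / 2² = 64.4, so 65 per group. At 66 per group, power is 90.7% (normal) or 90.3% (t). The figure reproduces, but it concerns mLK only. The documents give no event count, hazard ratio or power for revision surgery.

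**2. Is surgery analysed over time in all participants anywhere else?**

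| Place | Role of surgery | Estimates time to surgery in all randomised? |
|---|---|---|
| 3.2 | Endpoint named, unrestricted | No method given |
| 14.6, intercurrent events | Worst mLK score after surgery | No |
| 14.6, survival paragraph | Kaplan-Meier, log-rank, conditional Cox | Unilateral disease only |
| 14.7, responder analysis | Non-response if surgery before Week 52 | No |
| 14.7, Poisson rescue model | May count surgery, since 4.1 lists it among rescue options | No; a count that mixes surgery with drugs |

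**3. Illustration of size.** From the documents: 66 per arm and one revision per 42 months. Assumed: that rate as a constant placebo hazard, HR 0.5, equal event rates by laterality, no dropout, and a unilateral share of 10% to 60%.

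- Week 52 = 52 × 7 / 30.4375 = 11.96 months.
- Placebo risk = 1 − exp(−11.96/42) = 0.248.
- Dupilumab risk = 1 − exp(−0.5 × 11.96/42) = 0.133.
- Events in all randomised, E = 66 × (0.248 + 0.133) = 25.1.
- Schoenfeld power = Φ(|ln HR| × √(E/4) − 1.96). For E = 25.1: Φ(0.693 × 2.505 − 1.96) = Φ(−0.22) = 0.41.

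| Population | N | Events | Power | Share of events left out |
|---|---|---|---|---|
| All randomised | 132 | 25.1 | 41% | 0% |
| Unilateral 10% | 13 | 2.5 | 8% | 90% |
| Unilateral 20% | 26 | 5.0 | 12% | 80% |
| Unilateral 30% | 40 | 7.5 | 16% | 70% |
| Unilateral 50% | 66 | 12.6 | 23% | 50% |
| Unilateral 60% | 79 | 15.1 | 27% | 40% |

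The confidence interval for the log hazard ratio widens by 1/√share: 3.2 times at 10% and 1.3 times at 60%. With 2.5 events the approximation is rough.

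**4. Sensitivity to the assumed hazard ratio and follow-up.**

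| HR, cut-off | All randomised: events, power | Unilateral 10% to 60%: events, power |
|---|---|---|
| 0.3, Week 52 | 21.8, 80% | 2.2 to 13.1, 14% to 59% |
| 0.7, Week 52 | 28.3, 16% | 2.8 to 17.0, 5% to 11% |
| 0.5, Week 64 | 30.1, 48% | 3.0 to 18.1, 9% to 31% |

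**5. Consequence of the conditional Cox model.** Suppose a difference means a log-rank p-value below 0.05, which the plan does not say. At HR 0.5 and Week 52, the subgroup test would then miss it with probability 73% (100 − 27) to 92% (100 − 8), and no hazard ratio would follow.

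**The case against.** The strongest reply is that Section 3.2 already plans an unrestricted comparison of survival curves, and Section 14.5 puts all analyses under intention-to-treat. On this reading the survival paragraph in 14.6 is a supplementary laterality analysis, as the cross-reference from 5.2.1 suggests, and only a method is missing.

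Much of this stands. A reader might infer that the unilateral analysis is the only survival comparison planned, or that the objective is deliberately tested in the wrong population. The documents do not support either: 3.2 names the wider comparison, and 14.6 does not claim to be the test of that objective. Nor would an all-participant comparison be post hoc in itself; only the choice of its method would be.

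A reader might also infer that most events are left out, or that unilateral disease is atypical. Under equal event rates, the first holds only if fewer than half have unilateral disease, and no share is given. It would also be too strong to say that surgery has no planned estimate, because prevalence is an endpoint and the rescue model may count surgeries.

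These points do not close the gap. The intention-to-treat statement does not supply a time-to-event method. Section 3.2 keeps revision surgery separate from rescue medication, whose listed endpoints are corticosteroids and antibiotics. The mLK and responder analyses treat surgery as an intercurrent event.

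The low power is fair to raise and already disclosed: Section 14.10 says the trial is not designed for secondary outcomes. At HR 0.5, 80% power needs 66 events by Schoenfeld's formula, so the fix does not make this a well-powered test.

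**Conclusion.** The point holds as a mismatch between the endpoint in 3.2 and the methods in 14.6 and 14.7. The specified log-rank test omits all events in bilateral disease, and the conditional Cox model may leave the trial without a hazard ratio for surgery.

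On the base assumptions, the loss is from about 25 events (power about 41%) to about 2.5 to 15 events (power about 8% to 27%). The hazard ratio, constant hazard, equal event rates by laterality, absence of dropout and unilateral share are all assumptions. The 42-month figure is a background average, not a rate for these postoperative participants. The mismatch depends on none of them. It concerns an unpowered secondary endpoint and should be corrected before unblinding.

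**What to change.** In Section 14.7, specify:

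- Time from randomisation to revision sinus surgery, in all randomised participants, with Kaplan-Meier curves by arm.
- A log-rank test stratified by the randomisation factors. These must first be reconciled: Section 4.1 names site and baseline asthma, while Sections 4.7 and 14.4 name site only. With three sites and both factors there would be six strata, or about four events each (25/6).
- A Cox hazard ratio with 95% CI, reported whatever the p-value.
- A stated censoring time: Week 52, with Week 64 as supportive.
- The unilateral analysis kept as an exploratory subgroup.
- A statement that this unpowered secondary test lies outside the co-primary Bonferroni family, or its place within it. Section 14.6 does not define the family.

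The Schedule of Activities and Section 4.7.5 already provide for recording surgery and rescue therapy; the case report form should be checked for a surgery date in every participant. The cost is a short protocol amendment with IRB and DSMB review, and one more secondary test to place in the multiplicity plan.

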4.7 Randomization and blinding

Randomized participants will be stratified by enrollment site. Randomization will be assigned on a 1:1 basis to treatment group (dupilumab 300 mg every 2 weeks) or placebo. The study data team will prepare a randomization list based on computer-generated random numbers retrieved using a randomization procedure available in statistical packages such as SAS. Block randomization with varying block sizes will be employed to ensure that equal numbers of treatment and placebo participants occur within strata (site) and are balanced with respect to observed and unmeasured baseline factors.

This is a double-blind investigation. Patients, treating physicians and local study personnel will not be aware of cohort allocation.

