14.1 Sample Size and Power analysis

A sample size of 66 participants per group achieves 90% power to detect a mean difference of 2 points on the modified Lund-Kennedy Endoscopic score at 52 weeks with a standard deviation of 3.5 and significance level of 0.05 using a two-tailed test. The clinically meaningful mean difference of 2 points and the standard deviation are based on previous study of mLK in a heterogeneous population with nasal polyps [5].

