14.5 Statistical Approach

All data will first be assessed by the data management staff, under direction of the lead biostatistician, for missing data and out-of-range values with basic statistical procedures such as univariate statistics (means, standard deviations, ranges, frequencies, proportions, percentiles) and graphs such as histograms, box and whisker plots, scatter plots and Q-Q plots. In addition, plots may be produced of individual and average trajectories of all repeated measures over time according to assigned treatment. All questions of data quality and integrity will be investigated before any statistical modeling, as complete and accurate data are essential for unbiased estimates and confidence intervals.

Baseline and demographic characteristics will be summarized overall for all participants and when applicable, by treatment group. Univariate summary statistics will be provided for continuous variables and frequencies for categorical variables. Graphical methods mentioned above will be used to examine distributions and identify potential influential points. Data transformations for variables may be considered. The balance of baseline measures across the two treatment groups will be compared using appropriate 2-sample tests, including Wilcoxon rank-sum and t-tests, and Fisher's exact and Pearson Chi-square tests. All analyses will be

conducted using SAS version 9.1 for Windows (SAS Institute, Inc., Cary, NC). All analyses will be two-tailed with significance level of 0.05 and conducted using the intention-to-treat principle.

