14.6 Primary Analysis

To examine changes in the co-primary outcomes, the modified Lund-Kennedy score and the incidence of oral corticosteroid utilization per participant, a mixed effects longitudinal model will be fit that includes group (dupilumab, placebo) as a between participants factor and time (randomization through post-treatment period) as a categorical within participants factor plus their interaction term. Time is treated as categorical so that we can use the group-time interactions with the time main effect to estimate and test intent-to-treat (ITT) group differences at each time point, with 52 weeks as our primary ITT test. As randomization is stratified by site, site will also be included in the model. This mixed effects model allows incorporation of a random intercept term for each subject, different numbers of measurements (in case a visit is skipped), and the choice of appropriate variance-covariance structure. The mixed model will also permit identification of any significant changes in the post-treatment period from 52 to 64 weeks. This primary mixed model will incorporate all subject's randomized.

The primary objective will be assessed by testing this null hypothesis: treatment with Dupilumab post-surgery is equivalent to treatment with placebo post-surgery at 52-week end of treatment. The additional time point at 64 weeks is included in the model to ensure efficient evaluation of both co-primary outcomes at the EOT and 12 weeks after EOT. Significant changes between weeks 52 and 64 will be examined by linear contrast. We will test the following null hypotheses against two-sided alternatives:

- H₀₁: there is a lack of difference between the changes in mLK from baseline to 52 weeks and from baseline to 64 weeks for the untreated.
- H_{02} : there is a lack of difference between the changes in mLK from baseline to 52 weeks and from baseline to 64 weeks for the treated.
- H_{03} : the treatment effect dissipates between 52 and 64 weeks.

The primary estimand for the primary endpoint is the composite/treatment policy strategy. The intercurrent events will be handled as follows:

- Undergoing sinus surgery for AFRS: data after surgery will be assigned the worst possible score (composite strategy)
- Taking SCS or other rescue medications: data collected after use will be used in the analysis (treatment policy strategy)

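### If each co-primary can be claimed alone, Holm's step-down would hold the same family-wise error as the planned plain Bonferroni and is never less powerful; the gain is modest and depends on unstated oral corticosteroid (OCS) inputs

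*Combined protocol and SAP*

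**What the plan says.** Section 14.6 (Primary Analysis) begins with two outcomes: "To examine changes in the co-primary outcomes, the modified Lund-Kennedy score and the incidence of oral corticosteroid utilization per participant". It tests group differences at each time point from a longitudinal model, "with 52 weeks as our primary ITT test". The same section then lists H01 to H03, which concern Weeks 52 to 64, under the words "We will test the following null hypotheses against two-sided alternatives", and adds a log-rank test in the unilateral-disease subgroup. It ends with one sentence on multiplicity: "The Bonferroni correction will be used to account for multiple testing and ensure Type-I error rate remains nominal".

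The section gives no family, number of tests or per-test alpha. It mentions no step-down procedure, and it does not say whether success needs both co-primaries or only one.

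Elsewhere, section 14.5 states: "All analyses will be two-tailed with significance level of 0.05 and conducted using the intention-to-treat principle". Section 14.1 sizes the trial on mLK alone, "with a standard deviation of 3.5 and significance level of 0.05 using a two-tailed test". No effect size, variance or power is given for OCS use.

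**The concern.** If the family is the two Week-52 co-primary tests, plain Bonferroni holds each to 0.025 whatever the other shows. A p-value between 0.025 and 0.05 on one outcome is then declared not significant even when the other is clearly positive. Holm tests the smaller p-value at 0.025 and, if that passes, the other at 0.05. The same data could then support a valid second claim.

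This matters because the plan hopes for more than one effect. Section 14.10 expects worse mLK scores and more frequent rescue medication on placebo. Rescue medication there is broader than OCS: section 4.1 also counts topical corticosteroids, antibiotics and revision surgery. Still, OCS use is a co-primary in its own right. The mLK power in section 14.1 was calculated at 0.05, so there is little to spare once alpha is split.

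**Working it through.** **Inputs from the documents.** Section 14.1: 66 per arm, difference 2 points, SD 3.5, two-sided 0.05, stated power 90%. Section 4.7: 1:1 allocation. Section 14.6: two co-primaries and a Bonferroni correction.

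**Assumptions, because the documents give no figure.** OCS power at two-sided 0.05 from 30% to 95%; correlation (rho) of the two test statistics from 0 to 0.8; both statistics approximately normal; the family is exactly the two Week-52 tests.

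**Step 1. Reproduce the stated power.** The expected test statistic is 2 / (3.5 x sqrt(2/66)) = 3.28. At two-sided 0.05, power = Phi(3.28 - 1.96) = 90.7% (noncentral t: 90.3%). The stated 90% is reproduced.

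**Step 2. Power at 0.025.** Phi(3.28 - 2.24) = 85.1% (noncentral t: 84.4%).

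**Step 3. Ceiling on Holm's gain for mLK.** Holm tests mLK at no more than 0.05, so the gain cannot exceed 90.7 - 85.1 = 5.6 points. That is reached only if OCS is almost certain to be rejected at 0.025.

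**Step 4. Error control.** If both nulls are true, Holm errs only when the smaller p-value is below 0.025, which has probability at most 2 x 0.025 = 0.05. If only one null is true, Holm rejects it only when its own p-value is below 0.05. Neither argument uses independence. In simulation with no effect on either outcome, the family-wise error was 0.050, 0.049 and 0.047 at rho 0, 0.3 and 0.5, the same for both procedures. With a true mLK effect and no OCS effect, the error on OCS was 0.046, 0.045 and 0.043 under Holm, against 0.025 under Bonferroni. Holm uses more of the permitted 0.05 but does not exceed it.

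**Step 5. One cell by hand: OCS power 80% at 0.05, rho 0.** OCS power at 0.025 is Phi(1.960 + 0.842 - 2.241) = 71.2%.
- mLK under Holm: 0.851 + (0.907 - 0.851) x 0.712 = 0.891, a gain of 4.0 points.
- Both under Bonferroni: 0.851 x 0.712 = 0.606.
- Both under Holm: 0.606 + 0.851 x (0.800 - 0.712) + (0.907 - 0.851) x 0.712 = 0.721, a gain of 11.4 points before rounding.
- At least one, either procedure: 1 - (1 - 0.851) x (1 - 0.712) = 0.957. Both procedures need the smaller p-value below 0.025, so this never differs.

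**Step 6. The grid.** Gain of Holm over Bonferroni in percentage points, for rho 0 / 0.3 / 0.5 / 0.8:

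| OCS power at 0.05 | Gain on mLK | Gain for both |
|---|---|---|
| 30% | 1.2 / 0.6 / 0.3 / 0.0 | 8.8 / 8.7 / 8.8 / 9.0 |
| 50% | 2.2 / 1.4 / 0.9 / 0.1 | 11.6 / 11.1 / 10.9 / 10.9 |
| 70% | 3.3 / 2.5 / 1.9 / 0.7 | 12.2 / 11.2 / 10.6 / 9.9 |
| 80% | 4.0 / 3.3 / 2.7 / 1.5 | 11.4 / 10.4 / 9.6 / 8.4 |
| 90% | 4.7 / 4.2 / 3.8 / 3.0 | 9.7 / 8.7 / 8.0 / 6.5 |
| 95% | 5.1 / 4.8 / 4.6 / 4.2 | 8.2 / 7.4 / 6.9 / 5.7 |

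**Step 7. Sensitivity to the family.** If H01-H03 are also covered, there are five tests, the single-step level is 0.05 / 5 = 0.01, and mLK power falls to 76.0%. The grid above would then not apply.

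**The case against.** The strongest reply is that Bonferroni is valid and simple, each outcome's verdict stands alone with a matching 97.5% interval, and preferring Holm is a matter of efficiency. That stands: nothing here is an error in the plan.

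Three further objections stand in part.

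- **The family is not stated.** A reader might infer that the plan applies Bonferroni to exactly the two co-primaries. That is the natural reading, since these are the named primary outcomes and Week 52 is the named primary test, but the text does not say so. The sentence could also cover H01-H03 and the log-rank test. Moving those outside the family would then be a separate loosening of the plan.
- **The success rule is not stated.** If either outcome is enough for trial success, Holm leaves the chance of success unchanged and helps only with the second claim. If both were required, no split would be needed: each could be tested at 0.05, with joint power of 0.907 x 0.800 = 72.6% in the cell worked above, against 72.1% under Holm. Choosing Bonferroni points to separate claims, and under separate claims Holm is the better choice.
- **Intervals.** An outcome gained through Holm has a p-value between 0.025 and 0.05, so its 97.5% interval includes no effect. That is awkward to report, though it does not invalidate the test.

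**Conclusion.** The point holds as an inexpensive improvement, conditional on a two-test family in which each co-primary may be claimed separately. On that footing Holm keeps the family-wise error at 0.05 and is never less powerful. Over the assumed range it adds 0 to 5 points on mLK, with a ceiling of 5.6, and about 6 to 12 points for showing both effects.

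A reader might infer firmer figures, such as a loss of 3-5 points on mLK and 7-12 on both. The documents do not support those as properties of this trial. They need OCS power of roughly 70-90% at 0.025 with correlation of at most 0.5, and the plan gives neither quantity. With OCS power of 50% or less at 0.05, the mLK gain is only about 0 to 2 points, although the gain for both remains about 9 to 12. Nor do the documents support reading this as a flaw in error control, or as a way to raise the chance of at least one positive co-primary.

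**What to change.** Replace the closing sentence of section 14.6 with:

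*The two Week-52 between-arm co-primary tests will be assessed by Holm's procedure at family-wise two-sided 0.05: the smaller p-value at 0.025 and, if it is significant, the other at 0.05; either outcome may be claimed on its own.*

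Then say where the remaining tests stand. If H01-H03 or the unilateral-disease log-rank test are meant to be covered by the present correction, either apply Holm across that full family or label them explicitly as supportive. Do not drop their protection silently.

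The cost is one amended sentence plus that clarification, made before unblinding, with no added participants, visits or data. Section 14.9 plans no interim analysis, so no other alpha allocation is affected. The downside is in reporting: simultaneous intervals that match Holm are less direct. If 97.5% intervals are given, state that one may include no effect for an outcome that Holm declares significant.
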